#### 6.1.2 ULTRASOUND MEASURE OF SKIN-TO-MUSCLE AND RELATED THICKNESSES

Subjects who consent to participate in the ultrasound sub-study will have both right and left deltoids and one (either) quadriceps measured. The precise site of the ultrasound

within the deltoid and quadriceps will align with where EP is administered. The ultrasound measure will be performed at each of those three body sites in two manners: with no pressure applied by the technician through the probe to the tissue and separately, and with EP-like pressure applied by the technician through the probe to the tissue and separately. The “EP-like pressure” is defined as a firm push against the skin resulting in puckering of the skin by the ultrasound probe. The rationale for the differing pressures is to determine if and how much the thickness being measured will change. For each body site and pressure, three triplicate measures will be performed. The type and number of ultrasound images and replicates taken for each body site for each patient would be as follows:

**Table 8. Type and Number of Ultrasound Images, by Muscle and Probe Pressure**

	Right Deltoid	Left Deltoid	Either Quadriceps	Total
No pressure of the ultrasound probe on tissue site	3	3	3	9
EP-like pressure of the ultrasound probe on tissue site	3	3	3	9
Total number of replicate measures	6	6	6	18

Ultrasound measures will be performed during the screening period, i.e. before enrollment and hence before any administrations of VGX-3100, and will thus include both enrolled and screen-failed subjects.

Locally stored images of each ultrasound measure will be measured via digitizer or simple scale to obtain the following cross-sectional distances, for each replicate image:

- Skin to muscle distance (i.e. depth of the beginning of the muscle) = “S-M”
- Skin to bone distance (i.e. depth of the beginning of the bone) = “S-B”
- Muscle thickness (i.e. distance of the beginning to end of the muscle) = “MT”, a calculated field with the following equation:

$$MT = “S-B” - “S-M”$$

The ultrasound measures will be performed on all screened patients in this trial, thus including both enrolled patients and ultimately screen-failed patients in these sub-analyses.

Last, each patient would be asked for their handedness, i.e. whether they are they right-handed, left-handed, or ambidextrous.

## 6.2 DURING TREATMENT PROCEDURES BY VISIT

Once eligibility has been confirmed, the subject will be randomized to receive study treatment. Visit dates and windows must be calculated from Day 0.

### 6.2.1 DAY 0

The following evaluations will be performed on Day 0 **prior to study treatment**:

- Determination of eligibility per Inclusion/Exclusion Criteria

- Review of concomitant medications and adverse events
- Randomization
- Patient Reported Outcomes
- Targeted physical assessment
- Vital signs
- Urine pregnancy test
- Whole blood and serum for immunologic assay
- OP rinse, vaginal and intra-anal swabs
- Baseline vulvoscopy
- Vulvar lesion photography

Study treatment will be administered and the following evaluations will be performed on Day 0 **after study treatment**:

- Post treatment AE and injection site reaction assessment within 30-45 minutes after study treatment
- Distribute Participant Diary (PD)
- Distribute 1 box of imiquimod and the imiquimod dosing log (for subjects in the imiquimod arm)

Download EP data from device within 24 – 48 hours of study treatment

#### 6.2.2 8-14 DAYS POST DOSE 1 PHONE CALL

- Review Adverse Events
- Patient Reported Outcomes
- Review Day 0 PD
  - After completing a review of PD and post treatment injection assessment with the subject on the phone, the Investigator or study personnel will determine whether an office visit is needed for further evaluation.

#### 6.2.3 WEEK 4

The following study evaluations will be performed at Week 4 **prior to study treatment (± 7 days)**:

- Review of concomitant medications and adverse events
- Targeted physical assessment
- Vital signs
- Review imiquimod dosing log and usage (accountability of returned product) for subjects in the imiquimod arm
- Urine pregnancy test

- Vulvoscopy
  - Vulvoscopy visualization of a normal appearing vulva is insufficient evidence to confirm disease regression.
- Vulvar lesion photography
  - Photographs of the vulva and the associated lesion must be collected.

The following study evaluations will be performed at Week 4 **after study treatment**:

- Post treatment injection site reaction assessment within 30-45 minutes after study treatment
- Patient Reported Outcomes
- Distribute PD
- Distribute 1 box of imiquimod and the imiquimod dosing log (for subjects in the imiquimod arm)

Download EP data from device within 24 – 48 hours of study treatment

#### 6.2.4 8-14 DAYS POST DOSE 2 PHONE CALL

- Review Adverse Events
- Patient Reported Outcomes
- Review Week 4 PD
  - After completing a review of PD and post treatment injection assessment with the subject on the phone, the Investigator or study personnel will determine whether an office visit is needed for further evaluation.

#### 6.2.5 WEEK 12

The following study evaluations will be performed at Week 12 **prior to study treatment (± 7 days)**:

- Review of concomitant medications and adverse events
- Targeted physical assessment
- Vital signs
- Review imiquimod dosing log and usage (accountability of returned product) for subjects in the imiquimod arm
- Urine pregnancy test
- Vulvoscopy
  - An additional visit may be scheduled to perform vulvoscopy if worsening of disease is suspected. Biopsies should not be performed at any visit other than at entry (screening), Week 48, Week 74 and Week 94 unless PI suspects disease progression. All biopsy samples must be sent to the PAC for review
  - Vulvoscopy visualization of a normal appearing vulva is insufficient evidence to confirm disease regression

- Vulvar Lesion Photography
  - Photographs of the vulva and the associated lesion must be collected.

The following study evaluations will be performed at Week 12 **after study treatment**:

- Post-treatment injection site reaction assessment within 30-45 minutes after study treatment
- Patient Reported Outcomes
- Distribute PD
- Distribute 1 box of imiquimod and the imiquimod dosing log to subjects in the imiquimod arm

Download EP data from device within 24 – 48 hours of study treatment

#### 6.2.6 WEEK 15

The following study evaluations will be performed at Week 15 ( $\pm 7$  days):

- Review Adverse Events
- Review Week 12 Participant Diary
- Patient Reported Outcomes
- Whole blood and serum for immunologic assay

#### 6.2.7 WEEK 24

The following study evaluations will be performed at Week 24 **prior to study treatment ( $\pm 7$  days)**:

- Review of concomitant medications and adverse events
- Review imiquimod dosing log and usage (accountability of returned product) for subjects in the imiquimod arm
- Targeted physical assessment
- Vital signs
- Urine pregnancy test

The following study evaluations will be performed at Week 24 **after study treatment**:

- Post-treatment injection site reaction assessment within 30-45 minutes after study treatment
- Patient Reported Outcomes
- Distribute PD

Download EP data from device within 24 – 48 hours of study treatment

### 6.2.8 WEEK 27

The following study evaluations will be performed at Week 27 ( $\pm$  7 days):

- Review of concomitant medications and adverse events
- Review Week 24 Participant Diary
- Targeted physical assessment
- Vital signs
- Patient Reported Outcomes
- Urine pregnancy test
- Whole blood and serum for immunologic assay
- Cervical cytology and ThinPrep™ for HPV type
- OP oral rinse, vaginal and intra-anal swabs
- Vulvoscopy
  - An additional visit may be scheduled to perform vulvoscopy if worsening of disease is suspected. Biopsies should not be performed at any visit other than at entry (screening), Week 48, Week 74 or Week 96 unless the PI suspects disease progression. All biopsy samples must be sent to the PAC for review
  - Vulvoscopic visualization of a normal appearing vulva is insufficient evidence to confirm disease regression.
- Vulvar lesion photography
  - Photographs of the vulva and the associated lesion must be collected.

### 6.2.9 WEEK 38 PHONE CALL

- Review concomitant medications and adverse events

### 6.2.10 WEEK 48

The following study evaluations will be performed at Week 48 ( $\pm$  7 days):

- Targeted physical assessment
- Vital signs
- Review of concomitant medications and adverse events
- Socio-Behavioral Assessment; including self-reported smoking history, self-reported exposure to second-hand smoke, self-reported alcohol intake history, contraceptive history
- Urine pregnancy test

- Whole blood and serum for immunologic assay
- Cervical cytology and ThinPrep™ for HPV type
- OP oral rinse, vaginal and intra-anal swabs
- Vulvoscopy
  - Visualization of a normal appearing vulva by vulvoscopy is insufficient evidence to confirm disease regression.
- Vulvar lesion photography
  - Photographs of the vulva and the associated lesion must be collected.
- Vulvar biopsy or wide excision as per investigator discretion:
  - All biopsy samples must be sent to the PAC for review
  - Slides from all excised tissue must be reviewed by the PAC
    - If residual vulvar tissue is available from entry and/or Week 48 specimen(s) either paraffin blocks or unstained slides should be sent to the central pathology laboratory for IHC and testing for presence of HPV-16 and HPV-18
- Patient Reported Outcomes

#### 6.2.11 WEEK 52

Subjects will have a Week 52 consultation ( $\pm$  14 days) to discuss their biopsy results and treatment plan. The following assessments will also be performed:

- Review of concomitant medications and adverse events
- Targeted physical assessment
- Vital signs
- Patient Reported Outcomes
- Urine pregnancy test (for subjects receiving a 5th dose only)

Subjects receiving a 5th dose will have the following evaluations performed at Week 52 **after** study treatment:

- Post-treatment injection site reaction assessment within 30-45 minutes after study treatment
- Distribute Participant Diary

Download EP data from device within 24 – 48 hours of study treatment

#### 6.2.12 WEEK 74

The following study evaluations will be performed at Week 74 ( $\pm$  14 days):

- Review of concomitant medications and adverse events

- Review Week 52 Participant Diary
- Targeted physical assessment
- Vital signs
- Patient Reported Outcomes
- Urine pregnancy test
- Whole blood and serum for immunologic assay
- Cervical cytology and ThinPrep™ for HPV type
- OP oral rinse, vaginal and intra-anal swabs
- Vulvoscopy
  - Visualization of a normal appearing vulva by vulvoscopy is insufficient evidence to confirm disease regression.
- Vulvar lesion photography
  - Photographs of the vulva and the associated lesion must be collected.
- Vulvar biopsy or wide excision as per investigator discretion:
  - All biopsy samples must be sent to the PAC for review
  - Slides from all excised tissue must be reviewed by the PAC

If residual vulvar tissue is available either paraffin blocks or unstained slides should be sent to the central pathology laboratory for IHC and testing for presence of HPV-16 and HPV-18

### 6.2.13 WEEK 78

Subjects will have a Week 78 consultation ( $\pm$  14 days) to discuss their biopsy results and treatment plan. The following assessments will also be performed:

- Review of concomitant medications and adverse events
- Targeted physical assessment
- Vital signs
- Urine pregnancy test (for subjects receiving a 6th dose only)

Subjects receiving a 6th dose will have the following evaluations performed at Week 78 **after** study treatment:

- Post-treatment injection site reaction assessment within 30-45 minutes after study treatment
- Distribute Participant Diary

Download EP data from device within 24-48 hours of study treatment

#### 6.2.14 WEEK 96

The following study evaluations will be performed at Week 96 ( $\pm$  14 days):

- Review of concomitant medications and adverse events
- Review Week 78 Participant Diary
- Targeted physical assessment
- Vital signs
- Patient Reported Outcomes
- Urine pregnancy test
- Whole blood and serum for immunologic assay
- Cervical cytology and ThinPrep™ for HPV type
- OP oral rinse, vaginal and intra-anal swabs
- Cervical colposcopy
  - Photographs during colposcopic examinations of the vagina and/or cervical areas should be obtained if lesions are identified.
- Vulvoscopy
  - Visualization of a normal appearing vulva by vulvoscopy is insufficient evidence to confirm disease regression.
- Vulvar Lesion Photography
  - Photographs of the vulva and the associated lesion must be collected.
- Vulvar biopsy or wide excision as per investigator discretion:
  - All biopsy samples must be sent to the PAC for review
  - Slides from all excised tissue must be reviewed by the PAC

If residual vulvar tissue is available either paraffin blocks or unstained slides should be sent to the central pathology laboratory for IHC and testing for presence of HPV-16 and HPV-18

#### 6.2.15 WEEK 100

The following study evaluations will be performed at Week 100 ( $\pm$  14 days):

- Review of concomitant medications and adverse events
- Socio-Behavioral Assessment; including self-reported smoking history, self-reported exposure to second-hand smoke, self-reported alcohol intake history, contraceptive history
- Targeted physical assessment

- Vital signs
- Urine pregnancy test

## **6.3 EVALUATIONS AND PROCEDURES**

### **6.3.1 INFORMED CONSENT**

All subjects must sign the informed consent prior to any study related procedures being performed (i.e., prior to any screening activities). The informed consent documentation must be in accordance with applicable regulations and GCP. Qualified study personnel will meet with prospective study subjects, explain the study, and provide them with an informed consent form (ICF) that describes the screening tests, eligibility criteria for entering the study, study treatments and follow-up procedures, in a language understandable to the subject. Explanation of the study includes, but is not limited to, study objectives, potential benefits and risks, discomforts/inconveniences, and the subject's rights and responsibilities. The subject is then requested to sign and date the ICF. A copy of the signed informed consent documentation must be provided to the subject. The qualified study personnel will document the process of obtaining informed consent within the source record. Signed ICFs are maintained in the subject's source records and must be accessible for verification at any time.

### **6.3.2 ASSIGNMENT OF SUBJECT IDENTIFICATION NUMBERS**

Each subject who consents will be assigned a unique subject identification number (SID), which identifies the subject for all study-related procedures. SIDs are a combination of a up to two alpha letters study code, two alpha letter Country code, two digit site number, plus 3-digit subject number starting with 001 (e.g., VNUS01001). Once assigned, SIDs cannot be reused for any reason. Information regarding the SID and screen date must be documented on a Screening log/system and in the Interactive Response Technology (IXRS).

Subjects meeting eligibility criteria will be randomized by a computer generated allocation schedule.

### **6.3.3 SAFETY EVALUATIONS**

#### **6.3.3.1 PHYSICAL EXAMINATION**

A full physical examination (PE) will be conducted during screening and study discharge (Week 100). It will include an assessment of the following: general appearance, skin, head, eyes, ears, nose, and throat, and lymph nodes, and respiratory, cardiovascular, gastrointestinal, genitourinary, musculoskeletal, and neurological systems.

A targeted physical assessment will be performed at other visits as determined by the investigator or directed per subject complaints.

#### **6.3.3.2 VITAL SIGNS**

Vital signs will be measured at specified visits and will include:

- Sitting systolic and diastolic blood pressures with subject sitting at rest for at least 5 minutes before measurement
- Respiration rate
- Heart rate
- Oral temperature measured with an automated thermometer

#### 6.3.3.3 WEIGHT AND HEIGHT

Weight will be measured at all dosing visits and at screening, and height will be measured at screening to assess BMI.

#### 6.3.3.4 MEDICAL HISTORY

Medical history, including smoking history and gynecologic history, will be obtained at screening. All relevant (as judged by the investigator) past and present conditions, as well as prior surgical procedures will be recorded for the main body systems.

#### 6.3.3.5 SOCIO-BEHAVIORAL ASSESSMENT

Socio-Behavioral Assessment, including self-reported smoking history, self-reported history of exposure to second-hand smoke, self-reported alcohol intake history, self-reported recreational drug use history, self-reported history of contraceptive use and type of contraceptive if known, reproductive history, history of prior cervical dysplasia, and pregnancy history will be obtained at Screening.

At Weeks 48 and 100, socio-behavioral assessment will be performed to document any change from screening.

#### 6.3.3.6 LABORATORY EVALUATIONS

At screening, blood samples will be taken to be tested for serum chemistry and hematology.

##### Complete blood count (CBC):

- White blood cell (WBC) count with differential
- Red blood cell (RBC) count
- Hemoglobin, Hematocrit
- Platelet count

##### Serum Chemistry:

- Glucose
- Alanine aminotransferase (ALT)
- Blood urea nitrogen (BUN)
- Creatinine
- Electrolytes (Sodium, Potassium, Chloride, Carbon Dioxide or Bicarbonate)
- Creatine Phosphokinase (CPK)

#### Urinalysis (UA):

Urine samples will be tested at screening by dipstick for glucose, protein, and hematuria. If abnormal (presence of protein, hematuria, or glucose  $\geq 1+$ ) a microscopic examination should be performed.

#### **6.3.3.7 PREGNANCY TESTING**

For subjects of reproductive potential, a negative spot urine pregnancy test is required at screening, and prior to each study treatment, vulvoscopy and surgical excision or biopsy.

#### **6.3.3.8 ELECTROCARDIOGRAM (ECG)**

A single 12-lead ECG will be obtained during Screening after the subject has been in a supine position for 10 to 15 minutes. The ECG should include measurements of ventricular rate, PR, QRS, QRS axis, QT, QTcb or QTcf, ST segment, Twave as well as an investigator assessment of whether the ECG is normal or abnormal (automated interpretations of ECG should not be used). Abnormal ECGs should be interpreted as “clinically significant (CS)” or “not clinically significant (NCS)” by the investigator.

#### **6.3.3.9 POST-TREATMENT REACTION ASSESSMENTS**

The PD will capture subject reported local and systemic events for 7 days after the study treatment.

The subject will be provided a PD and will be asked to record the following the evening of study treatment through Day 6:

- Oral temperature and time taken (before 11:59 pm)
- General symptoms of feeling unwell
- Pain and itching at injection site
- Measure redness, swelling, bruising at injection site
- Medications taken

The completed PD will be reviewed with the subject and research staff at 8 -14 Days post-dose.

The study staff will review the PD for general symptoms (e.g. malaise, fatigue, headache, nausea, and myalgia/arthralgia), injection site reaction symptoms (e.g. pain, erythema and edema), medical events and medications. All reported events will be assessed for clinical significance (CS) and reported as adverse event accordingly.

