### 7.3.1 ADVERSE EVENTS OF SPECIAL INTEREST

Adverse events of special interest (AESI) are the adverse events deemed related to VGX-3100 delivered with CELLECTRA® 2000 that require expedited communication from the site to the Sponsor and meet any of the following criteria:

- Grade 3 or greater persistent administration site erythema, and/or induration recorded  $\geq 2$  hours immediately after Study Treatment
- Grade 4 or greater persistent administration site pain, tenderness recorded  $\geq 2$  hours immediately after Study Treatment
- Grade 3 or greater fever
- Grade 3 or greater systemic symptoms, including generalized pruritus
- Grade 3 or greater laboratory abnormalities

As per the Toxicity Grade for Healthy Adults. The most severe grade for that particular event is to be documented in the CRFs.

Sites will inform the Sponsor of an AESI within 24 hours via method described in [Section 7.4.2](#), to discuss whether further dosing should continue.

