## 2.2 SECONDARY OBJECTIVES AND ASSOCIATED ENDPOINTS

Secondary Objectives	Associated Secondary Endpoints
1. Evaluate the safety and tolerability of VGX-3100 delivered IM followed by EP with CELLECTRA® 2000, alone or in combination with imiquimod	1a. Local and systemic events for 7 days following each dose as noted in the Participant Diary. 1b. All adverse events including SAEs, SUSARs, UADEs, and other unexpected AEs for the duration of the study (through Week 100 visit)
2. Determine the efficacy of four doses of VGX-3100, alone or in combination with imiquimod, as measured by histologic regression of vulvar HSIL	2. Proportion of subjects with no evidence of vulvar HSIL on histology (i.e. biopsies or excisional treatment) at Week 48 visit
3. Determine the efficacy of four doses of VGX-3100, alone or in combination with imiquimod, as measured by virologic clearance of HPV-16/18 in vulvar tissue	3. Proportion of subjects with no evidence of HPV-16/18 in vulvar tissue samples at Week 48 visit
4. Determine the efficacy of VGX-3100 , alone or in combination with imiquimod, as measured by histologic regression of vulvar HSIL to normal tissue	4. Proportion of subjects with no evidence of vulvar HSIL and no evidence of condyloma on histology (i.e. biopsies or excisional treatment) at the Week 48 visit
5. Determine the efficacy of four doses of VGX-3100 , alone or in combination with imiquimod, as measured by non-progression of vulvar HSIL to vulvar cancer as determined by histology	5. Proportion of subjects with no progression of vulvar HSIL to vulvar cancer from baseline to Week 48 visit

 No evidence of vulvar HSIL is defined as normal tissue or vulvar LSIL (VIN 1) or condyloma

 Clearance of HPV-16 or HPV-18 is defined as being undetectable by PCR assay.

 Progression is defined as advancement to carcinoma according to the Pathology Adjudication Committee by histology.

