**Table 9. Summary of Reported Adverse Events and Potential Risks of VGX-3100 Delivered IM EP with CELLECTRA® 2000**

Very Common	
 
• Mild to moderate injection site pain or tenderness
 
• Malaise/fatigue, myalgia, or headache in the first few days following injection
 
• Upper respiratory tract infection
 
• Brief muscle contractions which may be uncomfortable
 
• Nausea
 

Common	
 
• Arthralgia
 
• Injection site reactions such as erythema, pruritus, swelling, hematoma
 
• Anxiety related to the administration procedure
 

Less Common	
 
• Severe injection site pain or tenderness
 
• Vasovagal reaction/lightheadedness/dizziness related to the administration procedure
 
• Temporary bleeding at the injection site
 
• Rash following administration
 

Uncommon or rare	
 
• Injection site reactions such as laceration, induration, bruising/ecchymosis, or scab
 
• Infection at the injection site
 
• Muscle damage resulting in transient changes in creatine phosphokinase
 
• Transient changes in clinical laboratory values
 

Unknown frequency or theoretical potential risks	
 
• Severe localized administration site reaction, such as sterile abscess or secondary bacterial infection
 
• Allergic reaction, including urticaria, angioedema, bronchospasm, or anaphylaxis
 
• Chills, flu-like syndrome
 
• Autoimmune disease
 
• Electrical injury
 
• Disruption of function of implanted electronic medical devices (if CELLECTRA® 2000 device is not used per User Manual)
 
• Exacerbation of unstable cardiac disease
 
• Effects on the fetus and on pregnancy
 

device only

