## 6.6 ASSESSMENT OF CLINICAL STUDY ADVERSE EVENTS

The injection site will be assessed by study personnel prior to and between 30-45 minutes after each study treatment. Subjects will be advised to record local and systemic AEs for 7 days after each study treatment on a PD which will be reviewed with study personnel at 8 – 14 days after dose 1 and 2, and at Weeks 15, 27, 74, and 96.

An assessment will be conducted at each visit during which subjects will be queried regarding the occurrence of any adverse events, concomitant medications new onset illness or disease, as well as contraceptive compliance. Subjects will be reminded to contact study personnel and immediately report any event that happens for the duration of the study. Unsolicited adverse events will be captured from the time of the informed consent to study discharge. These events will be recorded on the subject's CRF.

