**Table 12. Grading Scale for Injection Site Reactions**

Local Reaction to Injectable Product (Grade)	Mild (1)	Moderate (2)	Severe (3)	Potentially Life Threatening (4)
Pain	Does not interfere with activity	Repeated use of non-narcotic pain reliever >24 hours or interferes with activity	Any use of narcotic pain reliever or prevents daily activity	Emergency room (ER) visit or hospitalization
Tenderness	Mild discomfort to touch	Discomfort with movement	Significant discomfort at rest	ER visit or hospitalization
Erythema/Redness*	2.5-5 cm	5.1-10 cm	>10 cm	Necrosis or exfoliative dermatitis
Induration/Swelling**	2.5-5 cm and does not interfere with activity	5.1-10 cm or interferes with activity	>10 cm or prevents daily activity	Necrosis

September 2007 "FDA Guidance for Industry—Toxicity Grading Scale for Healthy Adult and Adolescent Volunteers Enrolled in Preventive Vaccine Clinical Trials"

\*In addition to grading the measured local reaction at the greatest single diameter, the measurement should be recorded as a continuous variable

\*\*Induration/Swelling should be evaluated and graded using the functional scale as well as the actual measurement

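### The diary items behind safety endpoint 1a omit injection-site tenderness, so Grade 1 to 3 tenderness over the 7 days may be under-captured

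*Protocol*

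**What the plan says.** Endpoint 1a in Protocol 2.2 is "Local and systemic events for 7 days following each dose as noted in the Participant Diary". Section 6.3.3.9 lists what the woman is asked to record from the evening of treatment through Day 6. The list covers temperature, feeling unwell, "Pain and itching at injection site", "Measure redness, swelling, bruising at injection site", and medications taken. Staff then review the diary for general symptoms and for "injection site reaction symptoms (e.g. pain, erythema and edema), medical events and medications". Neither list names tenderness.

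Table 12, which 6.7 tells investigators to use for injection-site reactions, has four rows: pain, tenderness, erythema/redness and induration/swelling. Grade 3 tenderness is "Significant discomfort at rest". Table 9 has "Mild to moderate injection site pain or tenderness" among the very common reactions.

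On timing, 6.6 says: "The injection site will be assessed by study personnel prior to and between 30-45 minutes after each study treatment". It also gives a general instruction to record local and systemic events in the diary for 7 days, and provides for an adverse event query at each visit.

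The version 1.2 text at hand stops at 6.12. Sections 7.1.7, 7.3.1, 7.3.2 and 8.11.1 are therefore read from version 1.1.

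**The concern.** The protocol defines a graded reaction, expects it to be frequent in combination with pain, and names the diary as the source of the 7-day endpoint. The diary's item list does not ask about it. A reaction that is not specifically asked about tends to be reported less completely than one that has its own daily line.

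Two things are at stake. One is the completeness of the local-reaction data in a secondary safety endpoint. The other is the count of related Grade 3 events. Under 3.3.1, three subjects with the same related Grade 3 or 4 event halt enrolment and treatment. Under 4.3.1, a related Grade 3 toxicity prompts a discussion of whether that woman continues. Both rules depend on Grade 3 reactions being recorded.

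**Working it through.** No sample size, power or rate enters this point, so the check sets the sections side by side.

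**Step 1: match the scale to the diary.**

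| Table 12 row | Graded by | Diary item in 6.3.3.9 |
|---|---|---|
| Pain | Limits on activity, analgesic use | Yes |
| Tenderness | Discomfort on touch, on movement, at rest | None |
| Erythema/redness | Diameter | Yes (redness, measured) |
| Induration/swelling | Diameter and function | Yes (swelling, measured) |

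Three of four rows are covered.

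**Step 2: can the pain item stand in for tenderness?** Not reliably, because the two rows use different criteria. Take a woman with significant discomfort at rest who needs no pain relief and carries on with her normal activity. She has Grade 3 tenderness. If the same experience is entered as pain, it does not interfere with activity and is Grade 1. At the other end, a site that is sore only when touched is Grade 1 tenderness and may produce no pain entry at all.

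**Step 3: which other routes reach tenderness after dosing?**
- The staff check at 30 to 45 minutes covers that moment only.
- The calls 8 to 14 days after doses 1 and 2 (6.2.2, 6.2.4) include diary review and a post-treatment injection assessment by phone.
- The diary carries a general instruction to record local events.
- Staff ask about any adverse event at each visit.

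All routes after the first are open prompts rather than a tenderness question. For later doses, 6.6 places diary review at Weeks 15, 27, 74 and 96. The nominal gaps are:
- dose 3: 15 − 12 = 3 weeks
- dose 4: 27 − 24 = 3 weeks
- dose 5: 74 − 52 = 22 weeks
- dose 6: 96 − 78 = 18 weeks

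An open question that long after dosing is unlikely to recover mild tenderness that was never written down.

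**Step 4: how many dose occasions are involved?** At most 36 × 4 = 144 for the four planned doses. The ceiling would be 36 × 6 = 216 if every woman also received the optional fifth and sixth doses, which are open only to Subgroups C and D. These figures count occasions. They do not estimate missed events.

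**Step 5: the reverse mismatch.** Itching and bruising are diary items but have no Table 12 row. Section 7.1.7 names two scales: the 2007 FDA scale (the source of Table 12) for injection-site reactions, and CTCAE v4.03 for other clinical events. Which one grades itching and bruising is not stated.

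**The case against.** The strongest reply is that tenderness is far from uncollected. The diary is meant to capture local events generally, the staff review list is open-ended, the calls after doses 1 and 2 include an injection-site assessment, and every visit has an adverse event query. Endpoint 1a does not specify a tenderness rate, and the main safety summary in 8.11.1 uses 14 days, with 7 days as a separate summary. Table 9 combines pain with tenderness, so it gives no frequency for tenderness alone. Many women would enter discomfort on movement or at rest under pain, which leaves touch-only soreness as the likeliest loss.

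Much of this stands. It rules out saying that tenderness has no source at all, or that the 45-minute check is the only staff assessment. It does not close the gap, because open prompts are not equivalent to a daily item and a pain entry cannot be regraded as tenderness (Step 2).

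A reader might also infer that the trigger for adverse events of special interest in 7.3.1 has no data behind it. The documents do not support that. The criterion is "Grade 4 or greater persistent administration site pain, tenderness recorded" 2 hours or more after treatment, and Table 12 defines Grade 4 tenderness as an emergency room visit or hospitalization. General adverse event and serious adverse event collection would catch such an event without a diary line. These events must also reach the sponsor within 24 hours, and the diary is reviewed days to weeks later, so it could not be the timely route for any of them.

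**Conclusion.** The mismatch is real and modest. The listed diary items do not include tenderness, so Grade 1 to 3 tenderness after the 30 to 45 minute check depends on open prompts. The 7-day tenderness data may be under-captured, and so may Grade 3 tenderness counting toward 3.3.1. The version 1.1 pausing rules in 7.3.2 also count related Grade 3 events, so they share the dependence. The Grade 4 special-interest trigger is not affected.

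The size cannot be computed, because the protocol gives no tenderness rate and no reporting rate for unprompted symptoms. The conclusion assumes that the diary form follows the 6.3.3.9 list. The form is not shown, and if it already asks about tenderness, only the protocol text needs correcting. For itching and bruising, the fault is an unspecified choice between two named scales, not the absence of any scale.

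This is a cheap improvement. It is worth making before data collection, because a later analysis cannot restore entries that were never made.

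**What to change.** Add injection-site tenderness to the diary items in 6.3.3.9, asked in the terms of Table 12: to touch, on movement and at rest. In 6.7 and 7.1.7, state which of the two scales already named, the 2007 FDA scale or CTCAE v4.03, grades itching and bruising. Both sections need the sentence, because 7.1.7 currently sends injection-site reactions to the FDA scale.

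The cost is one extra diary line per day for 7 days per dose, plus a clarifying sentence in each of two sections. No dose, schedule or stopping threshold changes.
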